9.3.2. Study drug exposures

9.3.2.1. Cohort 1: PAXLOVID exposure

Exposure to PAXLOVID will be identified through the presence of NDCs on pharmacy dispensing claims:

- 00069034506
- 00069034530

- 00069108506
- 00069108530
- 00069110104
- 00069110120

Codes will be periodically reviewed for completeness and updated as necessary.

9.3.2.2. Cohort 2: Treated comparator only exposures

Exposure to remdesivir and bebtelovimab will be identified through the presence of drug administration codes (HCPCS):

- J0248 Injection, remdesivir, 1 mg
- Q0222 Injection, bebtelovimab, 175 mg
- M0222 Intravenous injection, bebtelovimab, includes injection and post administration monitoring
- M0223 Intravenous injection, bebtelovimab, includes injection and post administration monitoring in the home or residence; this includes a beneficiary's home that has been made provider-based to the hospital during the COVID-19 public health emergency

Codes will be periodically reviewed for completeness and updated in the SAP as necessary.

9.3.2.3. Cohort 3: Untreated comparator exposures

Exposure to COVID-19 therapies used to identify pregnancies that are ineligible for the Untreated Comparator cohorts will be identified through the presence of NDCs and/or administration codes. Detailed code lists for this cohort will be included in the SAP.

Codes will be periodically reviewed for completeness and updated in the SAP as necessary.

9.3.3. Covariates

9.3.3.1. Time periods

[figure not shown]
The following dates and time periods will be used (Figure 4):

- Index date the date of start of treatment (Cohorts 1 and 2) or COVID-19 diagnosis plus the treatment interval (Cohort 3)
- Baseline the 6 months prior to ECD through the index date, with potential variability in capture of time prior to EDC according to timing of treatment and COVID-19 diagnosis as described below. As an example, each patient with the same timing of an index exposure (eg, treatment/COVID-19 at Day 60 of pregnancy) will have the same amount of baseline, but by anchoring to treatment/COVID-19, there is

potential for variability in the baseline window length according to the timing of treatment or COVID-19 infection.

- For individuals with index dates during pregnancy, the baseline period includes the ECD (Figure 4A)
- o For individuals index dates prior to ECD (eg, PAXLOVID initiation 2 days prior to ECD), the baseline period ends prior to ECD (Figure 4B)
 - For these pregnancies, select characteristics at ECD will still be captured (ie, maternal age at ECD, calendar year of ECD)
- All available pre-pregnancy data all available data from 01 January 2016 onward
- First trimester/pregnancy the time between ECD and end of first trimester/end of pregnancy

Figure 4. Time Periods for the Assessment of Covariates.

The baseline window will be defined using the first eligible treatment or COVID-19 diagnosis during an exposure window. Descriptive characteristics that capture the total number of COVID-19 therapies (eg, multiple courses of PAXLOVID) will be described during the first trimester/pregnancy window.

9.3.3.2. Covariates

All members of the study cohorts will be classified according to covariates identified in the claims data. Note that only baseline (ie, pre-treatment) covariates will be considered for inclusion in the propensity score models. Covariates assessed during pregnancy, which may occur after treatment initiation or infection, will be described and/or used for subgroup analysis. Recognizing that a narrower (for time-varying covariates, etc.) or broader (for chronic conditions, etc.) window of assessment may better capture select patient attributes of

interest, specific covariates may be assessed using alternate time period(s), which are noted below.

In addition to the covariates listed below, Optum will identify baseline predictors on an empiric basis by examining the most frequently occurring diagnoses, drugs dispensed, and procedures performed among pregnancies with and without PAXLOVID exposure. These empiric covariates will be considered for inclusion in the propensity score models used for IPTW.

Detailed definitions and code lists for covariates will be included in the SAP.

9.3.3.2.1. Baseline covariates

- Demographics including age, geographic area, and month and year of ECD (at the time of ECD)
- Healthcare utilization
 - Length of health plan enrollment
 - Number of physician visits, emergency room visits, and hospitalizations (prior to and during pregnancy, separately)
- Vaccinations received (eg, Tdap)
- Diagnoses related to alcohol, recreational drug, and tobacco use
- Diagnoses associated with increased risk for evolution to severe COVID-19, and the subset with evidence of treatment (for select comorbidities)
- Diagnoses associated with increased risk for thromboembolic events
- Diagnoses related to contraindications for study drugs, including renal and hepatic impairment
- Receipt of medications listed as contraindications for study drugs, including drugs highly dependent on CYP3A for clearance and drugs with established or potentially significant interactions with PAXLOVID
- Receipt of COVID-19 vaccines through drug or procedure codes (Wong et al. 2022) (using all available pre-pregnancy data)
 - o Time since most recent COVID-19 vaccination
- Diagnoses associated with an increased incidence of the pregnancy outcomes such as prior history of pregnancy complications, obesity, hypertension, chronic kidney disease, diabetes, infection during pregnancy, and cardiovascular disease
- Prior COVID-19 (using all available pre-pregnancy data; prior to and during pregnancy, separately)

- Characteristics of COVID-19 episode (up to and including treatment initiation or COVID-19 diagnosis) associated with cohort medication exposure (if applicable), including:
 - Site of diagnosis (eg, inpatient/emergency room)
 - Gestational age at start of COVID-19 episode
 - Time to cohort-defining treatment initiation
 - Receipt of supplemental oxygen
 - Critical care indicators
- Calendar time (month and year) of index date (first COVID-19 treatment initiation or COVID-19 infection)
- Duration between index date and ECD (this value will be positive if the index event occurred after ECD, and negative if the index event occurred prior to ECD)

9.3.3.2.2. First trimester/Pregnancy covariates

- Prenatal care during pregnancy, including but not limited to:
 - Vaccines received
 - Number and timing of prenatal care visits
 - Ultrasound
- Receipt of COVID-19 vaccines through drug or procedure codes (Wong et al. 2022)
- COVID-19 diagnoses and episodes during pregnancy, including:
 - Number of COVID-19 diagnoses and episodes during pregnancy
 - Duration of COVID-19 episode(s)
 - Time between COVID-19 episodes
 - Use of specific therapies (Westhoff et al. 2022) during COVID-19 episode(s)
 - Hospitalization for COVID-19 episode(s)
- Total number of COVID-19 treatments received (eg, total days' supply, number of dispensings, etc.)
- Diagnoses and procedures related to COVID-19 sequelae such as acute respiratory distress syndrome
- Diagnoses associated with an increased incidence of adverse pregnancy outcomes such as infection during pregnancy and hospitalization during pregnancy (using all pre-pregnancy data)

• Other medication dispensings such as off-label COVID-19 therapies

9.4. Data sources

9.4.1. The Optum Research Database

The patients included in this study will be drawn from the ORD, a proprietary research database containing eligibility and pharmacy and medical claims data from a large US health plan affiliated with Optum. The individuals covered by this health plan are geographically diverse across the US. As early as 1993, medical and pharmacy claims data are available for 70 million individuals with both medical and pharmacy benefit coverage. For 2021, data are available for approximately 12.6 million individuals with medical and pharmacy coverage. Optum Epidemiology research activities utilize de-identified data from the research database. In limited instances, patient identifiers may be accessed where applicable law allows the use of patient-identifiable data, and when the study obtains appropriate approvals for accessing data that are not de-identified.

The data include demographics, details from pharmacy claims (reflecting dispensings), all medical and facility claims, including information on the types of services or procedures, and their accompanying diagnoses. The coding of medical claims conforms to insurance industry standards, including:

- Use of designated claims forms (eg, physicians use the Centers for Medicare & Medicaid Services [CMS]-1500 format and hospitals use the universal billing [UB]-04 format)
- ICD-10 diagnosis codes and procedure codes
- CPT codes³
- CMS HCPCS codes

Claims for pharmacy services are typically submitted electronically by the pharmacy at the time prescriptions are filled. These data allow for longitudinal tracking of medication refill patterns and changes in medications and include:

- NDC
- Drug name
- Dosage form
- Drug strength
- Fill date
- Days' supply

³ CPT copyright 2022 American Medical Association (AMA). All rights reserved.

- Cost information
- De-identified patient and prescriber codes

The machine-readable dataset of the ORD can be augmented on an ad hoc basis by further inquiry, including medical record review. The data are only re-identified following approval by an Institutional Review Board (IRB), and all data access conforms to applicable Health Insurance Portability and Accountability Act policies.

9.4.2. The Optum Dynamic Assessment of Pregnancies and Infants

The cohorts for this study will employ DAPI, a proprietary process that includes a set of capabilities and established algorithms that is applied to claims data to identify pregnancies, trimesters, and pregnancy outcomes, and to link mothers' and infants' data in an ongoing manner, within the ORD (Bertoia et al. 2022). The algorithms are based on a combination of validated algorithms as reported in the literature and clinical input. Mother and infant records will be linked through the presence of a common unique family insurance ID. This number is used by health plans to identify all members of a family who are covered by the same insurance plan for the purposes of defining coverage, payment, and reimbursement, providing assurance that mother-infant pairs identified in this manner are accurate. In addition, claim(s) relating to the delivery must be within 7 days of the infant's birthdate (or 32 days for multiples).

In comparison with the broader US population, the women of child-bearing age who are included in the ORD (and DAPI) tend to be healthier, reflecting the underlying population of the commercial insurance enrollees, and likely have an age distribution more skewed toward older age, reflecting the age distribution of women within the work force.

Historically, there are approximately 200,000 pregnancies identified each year within the database, of which 80% (with observed outcomes) result in livebirths, 85% of which can be linked to an infant within the database. These linkages enable proactive monitoring of pregnancy outcomes to ascertain a range of outcome-specific risks associated with drug exposure during pregnancy. This linkage has been used to address regulatory questions by pharmaceutical companies about the effects of drugs on pregnancy (Cole & Modell et al. 2007, Cole & Ephross et al. 2007, Carman et al. 2017, Wyszynski et al. 2016).

The fraction of identified deliveries that cannot be matched to an infant is likely due to the infant being covered under a different health insurance plan from the mother. This may occur if the infant were to be added to the other parent's plan (rather than the birth mother's), if the parents were to switch from individual plans to a family health plan, or if the mother were covered under her parent's policy (in which case a separate plan would need to be purchased for the infant). While the reasons for switching of the infants' health plans may be related to coverage for treatments relating to infant outcomes, reasons for switching are likely non-differential with respect to maternal exposure to COVID-19 treatments. Therefore, while estimates of risk or prevalence may be underestimated due to the switching of health plans, estimates of relative risk should be unbiased.

For a subset of women and infants, Optum can (with appropriate approvals) access medical records for mothers or infants in order to confirm outcomes.

9.4.3. Medical records

As noted in Section 9.3.1.3 (Medical Record Confirmation of Outcomes), medical records will be sought for the adjudication of select outcomes. The medical record adjudication results will be incorporated into the final report.

9.4.4. Multiple research partners

Optum has extensive experience as both a participating research partner and as the coordinating center for multi-partner studies, including pregnancy studies performed for regulatory purposes. The potential for small numbers of either PAXLOVID-exposed or comparator pregnancies may mean that multiple research partners are required to achieve adequate sample size to provide sufficient statistical power for analyses of the less common outcomes. Accrual of eligible pregnancies will be assessed following the third interim report, at which point the addition of research partners will be considered.

9.5. Study size

The planned sample size incorporates several assumptions derived from published literature, including the following approximate prevalence of pregnancy outcomes:

- Under 1% of pregnancies result in stillbirth (FDA 2002)
- 14% of pregnancies result in SA or miscarriage (FDA 2002)
- 18% of pregnancies have historically been expected to end in induced termination (Jones et al. 2017)
- 3% of live born infants have a major birth defect in the US each year (March of Dimes 2015)
- 10% of live born infants are born preterm or SGA (CDC 2008, Ferré et al. 2016)

Based on these reference percentages, the following assumptions were made for sample size calculation:

- $\alpha = 0.05$
- Power=0.8
- 1:2 matching
- Outcome prevalence as cited above

Table 1 and Table 2 show the minimum required number of PAXLOVID-exposed pregnancies required to proceed to the secondary objective of comparative analyses. Comparative analyses will be conducted if the sample size to detect a RR > 2.0 is achieved for each outcome; target sample size may be achieved for some outcomes but not others.

To detect a RR > 2.0 at 80% power a minimum of 127 PAXLOVID-exposed pregnancies are required for SA, 251 for SGA and preterm birth, and 2,212 for stillbirth, the rarest of the outcomes (Table 1). A minimum of 938 PAXLOVID-exposed pregnancies during the first trimester are required for the primary outcome of MCM (Table 2).

Fewer PAXLOVID-exposed pregnancies are required to detect an RR of > 2.5 at 80% power: 63 for SA, 127 for SGA and preterm birth, and 1,142 for stillbirth. For MCM, the minimum number of pregnancies with PAXLOVID exposure during the first trimester is 482. These estimates are based on 1:2 matching; however, the analyses for this study will utilize IPTW for confounding adjustment. Sample size calculations are based on 1:2 matching as a conservative estimate due to the retention of all eligible pregnancies in IPTW. Power for the analysis of induced termination will be similar to that for SA. The majority of pregnancies end in livebirth; therefore, power is expected to be adequate for this outcome.

Table 1. Sample Size Required for 80% Power to Detect Relative Risks (As or More Extreme) for Pregnancy Outcomes, with 1:2 Matching

Outcome	Prevalence of Outcome	RR	PAXLOVID-Exposed Pregnancies with Observed Outcomes Needed*	PAXLOVID-Exposed Pregnancies Needed**
SA	14%	2	101	127
		2.5	50	63
Stillbirth	1%	2	1,769	2,212
		2.5	913	1,142

^{*} Sample size calculated using PROC POWER function in SAS with a two-sided likelihood ratio chi-square test, and the specified relative risk and prevalence in the unexposed (SAS EG V8.2, SAS Institute Inc., Cary, NC).

Table 2. Sample Size Required for 80% Power to Detect Relative Risks (As or More Extreme) for Infant Outcomes, with 1:2 Matching

Outcome	Prevalence of Outcome	RR	PAXLOVID- Exposed Livebirths Needed*	PAXLOVID- Exposed Pregnancies Needed**
MCM	3%	2	572	938
		2.5	294	482
Preterm birth	10%	2	153	251
		2.5	77	127
SGA	10%	2	153	251
		2.5	77	127

^{**} A divisor of 0.80, which is the proportion of ongoing pregnancies for which an outcome is eventually observed in DAPI, was used to calculate the number of exposed pregnancies needed.

Table 2. Sample Size Required for 80% Power to Detect Relative Risks (As or More Extreme) for Infant Outcomes, with 1:2 Matching

Outcome	Prevalence of	RR	PAXLOVID-	PAXLOVID-
	Outcome		Exposed	Exposed
			Livebirths	Pregnancies
			Needed*	Needed**

^{*} Sample size calculated using PROC POWER function in SAS with a two-sided likelihood ratio chi-square test and the specified relative risk and prevalence in the unexposed (SAS EG V8.2, SAS Institute Inc., Cary, NC).

Following initial accrual results from the first interim report, it was observed that fewer Cohort 2 pregnancies were accrued than PAXLOVID-exposed pregnancies, at a ratio of approximately 5:1, suggesting that matching of 2 comparators to each PAXLOVID pregnancy is unlikely to be feasible. Assuming a final ratio of 5 PAXLOVID-exposed pregnancies to each Cohort 2 pregnancy, a minimum sample size of 3,352 PAXLOVID-exposed pregnancies (and 670 Cohort 2 pregnancies) will be required to be accrued during the first trimester exposure window to detect a RR \geq 2.0 at 80% power for MCM. To detect a RR \geq 2.5, 1,664 PAXLOVID-exposed pregnancies (and 333 Cohort 2 pregnancies) will be required.

Table 3 provides counts of total pregnancies, COVID-19 positive pregnancies, and pregnancies exposed to COVID-19 treatments within the ORD in 2020-2022. While 200,000 pregnancies are typically identified in any given calendar year within the ORD, this number has dropped slightly during the COVID-19 pandemic, as seen in Table 3 with roughly 180,000 pregnancies identified in 2020 and 2021. The counts include complete data through mid-2022; thus, some pregnancies in the latter half of 2022 may not be captured. Between 2020 and mid-2022, 35,303 of 460,062 pregnancies (7.7%) had a COVID-19 diagnosis code. Of the 35,303 COVID-19 positive pregnancies, 409 (1.2%) of pregnancies were exposed to bebtelovimab, while 382 (1.1%) were exposed to remdesivir. A total of 1,021 pregnancies were exposed to PAXLOVID, with roughly half of these also being diagnosed with COVID-19.

Annual interim reports will provide information on the uptake of PAXLOVID and the ability to reach adequate sample size for the study outcomes. If needed, a data partner may be added to increase statistical power (Section 9.4.4) to conduct the comparative analysis of MCM, per the secondary study objective. Even with multiple data partners, power may not be adequate for the assessment of stillbirth due to its rarity.

Table 3. Counts of Total and COVID-19 Positive Pregnancies in the Optum Research Database, 2020-2022

	2020	2021	2022	Total
			(partial) ^a	
All pregnancies	182,835	179,058	98,169	460,062

^{**} A divisor of 0.61, which is the proportion of ongoing pregnancies for which an outcome is eventually observed and the outcome is a livebirth in DAPI, was used to calculate the number of total exposed pregnancies needed.

^{***}Minimum sample size refers to the pregnancies with first trimester exposure

Table 3. Counts of Total and COVID-19 Positive Pregnancies in the Optum Research Database, 2020-2022

	2020	2021	2022	Total
			(partial) ^a	
Pregnancies with ≥1 PAXLOVID		295	726	1,021
dispensing				
Pregnancies with ≥1 COVID-19	10,337	19,581	5,385	35,303
diagnosis code				
Subset of pregnancies with ≥1		185	379	564
COVID-19 diagnosis code and ≥1				
PAXLOVID dispensing				
Subset of pregnancies with ≥1		184	225	409
COVID-19 diagnosis code and ≥1				
bebtelovimab administration				
Subset of pregnancies with ≥1	165	206	11	382
COVID-19 diagnosis code and ≥1				
remdesivir administration				

a Data for 2022 is approximately complete through June 2022.

This count is for informational purposes only. Final sample size for the study could change depending upon criteria applied during the application of the protocol, incomplete infant linkage, incomplete medical record retrieval, and required approvals.

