9. RESEARCH METHODS

9.1. Study design

This 5-year observational cohort study will use administrative healthcare claims data (the ORD) to assess PAXLOVID exposure and pregnancy and infant outcomes including SA, induced termination, stillbirth, livebirth, SGA, preterm birth, postnatal growth deficiency, and infant developmental delay and MCM. The primary outcome is MCM, which will be confirmed via medical record review. Pregnancies that begin (based on the ECD, equal to LMP + 14 days) between 01 March 2021 and 01 December 2025 will be identified. For the assessment of infant outcomes, pregnancies that begin on or before 01 April 2025 will be eligible for inclusion. Pregnancies that began in March 2021 are the earliest eligible PAXLOVID-exposed pregnancies in the US (ie, potentially exposed to PAXLOVID close to delivery in December 2021).

All qualifying pregnancies per woman will be included in the study and classified according to the COVID-19 treatments received during 2 relevant exposure windows:

- First trimester exposure window
- Full pregnancy exposure window

These 2 windows provide the flexibility to assess the timing of exposure during pregnancy, as the relevant etiologic period may be the first trimester for MCM whereas the full pregnancy may be the relevant exposure period for pregnancy or other infant outcomes. Given that COVID-19 treatment is typically administered shortly after COVID-19 diagnosis, these exposure windows will account for timing of COVID-19 during pregnancy as well.

[figure not shown]
Based on received COVID-19 treatments during each of 2 exposure windows (first trimester, pregnancy), the pregnancies will be classified into the following exposure cohorts (for a total of 6 cohorts):

- Cohort 1 (PAXLOVID cohorts): at least 1 dispensing of PAXLOVID within the relevant exposure window, and no evidence of comparator medications within the relevant exposure window
- Cohort 2 (Treated Comparator Only cohorts): no evidence in the study database of a dispensing of PAXLOVID, and dispensing or administration of at least 1 of the following treatments indicated for the treatment of mild-to-moderate COVID-19 within the relevant exposure window:
 - Remdesivir
 - Bebtelovimab
- Cohort 3 (Untreated Comparator cohorts): no evidence in the study database of a dispensing or administration of any COVID-19 treatments within the relevant exposure window

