9.2.3. Identification of pregnancy and estimation of LMP and ECD

Pregnancies will be identified using the Optum Dynamic Assessment of Pregnancies and Infants (DAPI) (Section 9.4.2). This process applies a set of algorithms comprised of International Classification of Diseases, 10th revision (ICD-10) diagnosis and procedure codes, Current Procedural Terminology¹ (CPT) codes, and HCPCS codes to the claims data to identify pregnancies, LMP date, pregnancy end date, and pregnancy outcome (Bertoia et al. 2022).

DAPI uses ICD-10 Z3A codes denoting weeks of gestation to estimate the LMP (Chomistek et al. 2021, Chomistek et al. 2022). The LMP date is the first day of the last menstrual period before pregnancy. Validation of Z3A-based LMP estimation has indicated good performance, with a median difference in days between LMP date based on Z3A codes and adjudicated (via medical record review) LMP date of 4.0 days (interquartile range: 2.0 – 10.0 days). Gestational age is anchored by the LMP date, where 12 weeks gestation is 12 completed weeks after LMP, 30 weeks gestation is 30 completed weeks after LMP, etc. Conception typically occurs about 2 weeks after the LMP date, around ovulation which is midway through the menstrual cycle. ECD will be calculated based on the estimated LMP (LMP + 14 days).

There is a small fraction of pregnancies that do not have Z3A codes; in these cases, DAPI assigns an average length of gestation for different pregnancy outcomes and uses that average length to estimate the accompanying ECD (eg, 39 weeks for full-term births and 10 weeks for all abortions), as described by Hornbrook et al. (Hornbrook et al. 2007). DAPI may be refined over the course of the project based on clinical input and review of published literature.

¹ CPT copyright 2022 American Medical Association (AMA). All rights reserved.

Fee schedules, relative value units, conversion factors and/or related components are not assigned by the AMA, are not part of CPT, and the AMA is not recommending their use. The AMA does not directly or indirectly practice medicine or dispense medical services. The AMA assumes no liability for data contained or not contained herein.

CPT is a registered trademark of the American Medical Association.

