9.2.6.1. Cohort 1: PAXLOVID cohorts

Pregnancies will be included in the PAXLOVID cohorts (Cohort 1) if they meet the following criteria:

1. Dispensing of outpatient PAXLOVID between 7 days prior to ECD and the end of the exposure window.

AND

- 2. None of the following:
 - a. Administration of remdesivir between 9 days prior to ECD and the end of the exposure window.

OR

b. Administration of bebtelovimab between 60 days prior to ECD and the end of the exposure window.

The 7-day pre-ECD window for PAXLOVID was chosen because of the 5-day recommended treatment course, plus 2 days to achieve 5x the clearance half-life. See Section 9.2.6.2 for justification for other pre-ECD windows.

Because the precise indication for PAXLOVID ("mild-to-moderate COVID-19") cannot be directly captured in claims data, and to improve comparability with comparator pregnancies, only PAXLOVID dispensings occurring in an outpatient setting will be eligible for inclusion.

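### The 127-pregnancy threshold for spontaneous abortion (SA) rests on an all-pregnancy risk of 14%, which is too high for cohorts entered at a treatment or COVID-19 index, so the stated 80% power does not hold

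*Protocol*

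**What the plan says.** Section 9.5 lists the outcome prevalences behind the sample size. For SA the entry is "14% of pregnancies result in SA or miscarriage (FDA 2002"). Table 1 uses this figure as the prevalence in the unexposed, and the text concludes: "To detect a RR > 2.0 at 80% power a minimum of 127 PAXLOVID-exposed pregnancies are required for SA". The abstract repeats the number. The number also decides whether the comparison is made: "Comparative analyses will be conducted if the sample size to detect a RR > 2.0 is achieved for each outcome". For terminations the section adds: "Power for the analysis of induced termination will be similar to that for SA".

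Cohort membership is defined elsewhere. Cohort 1 requires "Dispensing of outpatient PAXLOVID between 7 days prior to ECD and the end of the exposure window" (Section 9.2.6.1), and Cohorts 2 and 3 are built the same way on a comparator administration or a COVID-19 diagnosis. The pregnancy exposure window runs to the end of pregnancy (Section 9.2.5). SA is loss before week 20 (Section 9.3.1.1). The denominator for pregnancy outcomes is the cohort's pregnancies (Section 9.7.2.2), with no stated restriction to an index before week 20. Section 9.1 says the first trimester may be the relevant window for malformations, "whereas the full pregnancy may be the relevant exposure period for pregnancy or other infant outcomes". Section 9.5 ties only the malformation count to first-trimester exposure.

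**The concern.** The planning risk and the cohorts refer to different populations. The 14% counts losses among all pregnancies. A pregnancy lost early has few weeks in which to be treated or diagnosed, and one carried to term has many, so losses are under-represented in every full-pregnancy cohort, comparators included. The SA prevalence that the analysis will see is lower than 14%, and a relative risk of 2.0 on a lower base needs more pregnancies.

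The number is both a power statement and a decision rule. If it is too small, the SA comparison can open with well under 80% power, and a null result could be taken as adequately powered evidence against a doubling of risk in a safety study. The point concerns the planning prevalence, not where follow-up starts.

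**Working it through.** **Method.** The Table 1 footnote says: "Sample size calculated using PROC POWER function in SAS with a two-sided likelihood ratio chi-square test". With n₁ exposed at risk p₁ = RR × p₀, n₀ comparators at risk p₀, and pooled risk p̄, the noncentrality is λ = 2 Σ nᵢ [pᵢ ln(pᵢ/p̄) + (1 − pᵢ) ln((1 − pᵢ)/(1 − p̄))]. Power is the chance that a noncentral chi-square (1 df, λ) exceeds 3.84.

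**Reproducing the plan's figure.** At p₀ = 14%, p₁ = 28%, 101 is the exact answer for the smaller group when the exposed group is the larger one (202 exposed, 101 comparators: λ = 7.87, power 80.1%). Then 101/0.80 = 126.25, rounded up to 127. With one exposed to two comparators, as the table is labelled, the answer is 96, and 96/0.80 = 120. The direction of the ratio is a separate matter. Read as labelled, 101 v 202 gives λ = 8.32 and power 82%, so the label slightly favours the plan.

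**Power at the plan's numbers as the reference risk falls.** The last column is the size for RR 2.0, 80% power and 1:2, after division by 0.80.

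| SA risk in comparators | Power, RR 2.0 (101 v 202) | Power, RR 2.5 (50 v 100) | PAXLOVID pregnancies needed |
|---|---|---|---|
| 14% | 82% | 83% | 120 |
| 11% | 70% | 70% | 160 |
| 10% | 65% | 65% | 179 |
| 8% | 54% | 54% | 232 |
| 6% | 42% | 42% | 319 |
| 4.4% | 32% | 32% | 445 |
| 2% | 17% | 17% | 1,013 |

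**Where in this range the cohorts might fall.** The documents give neither the SA risk conditional on reaching index nor the distribution of gestational age at index. One illustration uses:

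- the Section 9.5 mix: 14% SA, 18% termination, 1% stillbirth, leaving 67% livebirth;
- the Section 9.2.3 lengths, "39 weeks for full-term births and 10 weeks for all abortions";
- my assumptions: a constant weekly chance of index from gestational week 1 (ECD minus 7 days), and stillbirth at 28 weeks.

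Weights are share × weeks available:

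- SA: 0.14 × 9 = 1.26
- Termination: 0.18 × 9 = 1.62
- Stillbirth: 0.01 × 27 = 0.27
- Livebirth: 0.67 × 38 = 25.46
- Total: 28.61

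Results:

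- Full pregnancy: 1.26/28.61 = 4.4% SA, power 32%.
- Index before week 20 only: 1.26/(1.26 + 1.62 + 0.68 × 19) = 1.26/15.80 = 8.0%, power 54%.
- First trimester ending at week 13: 1.26/(2.88 + 0.68 × 12) = 11.4%, power 72%.
- First trimester ending at week 14: 1.26/(2.88 + 0.68 × 13) = 10.8%, power 69%.

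Spreading losses over the risk period in three assumed shapes, with index uniform over weeks 2 to 39, gives 1.6% to 3.8% for full pregnancy (power 14% to 28%). With index before week 14 it gives 4.8% to 9.8% (power 35% to 64%).

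**A generous check.** Under the first illustration, 15.80/28.61 = 55% of full-pregnancy members are indexed before week 20. Give all of them the whole 14%, ignoring survival to index: 0.14 × 0.55 = 7.7%, power about 53%. For the cohort to show 14%, those indexed early would need a risk of about 0.14/0.55 = 25%.

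**The case against.** A reader might infer that 127 pregnancies give 32% power. The documents do not support a single figure. The 10-week length is a default for the small fraction of pregnancies without gestational-week codes and covers all abortions; it is not an observed mean SA timing. Other assumptions move the result both ways. The loss-timing shapes above give 14% to 28%. Using the 60-day bebtelovimab window in the same formula gives 6.4% SA and about 45% power. This objection stands: 32% is one illustration.

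A reader might also extend the large shortfall to all cohorts. The protocol compares by exposure window, and Section 9.1 says only that full pregnancy may be the relevant period. The first-trimester shortfall is modest if the SA risk there is about 11%.

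A third inference is that more accrual is needed. Against Cohort 3 this is unlikely. Table 3 counts 1,021 exposed pregnancies by mid-2022, before eligibility criteria. Taking 1,021 × 0.80 = 817 with outcomes against 1,634 comparators, power is about 99% at 4.4% and 80% at 2%. Cohort 2 is weaker, largely because of its roughly 5:1 ratio, a separate issue.

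Nor is the termination statement shown to be wrong. In the illustration termination is 1.62/28.61 = 5.7%, with 40% power against 32% for SA, so it remains at least as well powered and no separate row is shown to be necessary.

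Finally, Table 1 follows from its stated inputs, accrual is reviewed annually and results carry confidence intervals. That limits the harm, but it does not correct a stated power and a stated threshold.

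**Conclusion.** The point holds for the threshold and its power claim. Applied to the full-pregnancy cohorts, a 14% reference risk is too high and 127 pregnancies do not give 80% power for RR 2.0. The direction follows from the cohort and outcome definitions, provided that pregnancies with COVID-19 do not carry an SA risk far above the all-pregnancy figure; the documents give no such risk. The size can be stated only as a range: power from about 65% down to 17% for reference risks of 10% to 2%, and about 69% to 72% for first-trimester cohorts if their risk is about 11%. The 63-pregnancy figure for RR 2.5 (50 with observed outcomes) has the same fault, although it is not the number that opens the comparison. The practical consequence against Cohort 3 is limited by the counts already reached. What needs correcting is a threshold that passes too easily and a power statement that the cohorts cannot support.

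**What to change.** In Section 9.5, Table 1 and the abstract, replace the 14% with the SA prevalence expected among pregnancies that reach an index, separately for the first-trimester and full-pregnancy windows. The source is at hand: Section 9.7.1 already tabulates claims-based outcomes by cohort and exposure window in each interim report, and Cohort 3 supplies the reference. Then restate, for each window, either the number needed for RR 2.0 or the power available at 127, and use the restated figure as the threshold. Update the RR 2.5 figure in the same way, and base the induced-termination sentence on the same source in place of the 18%. Until those prevalences are inserted, a short table of power over a range of reference risks would be honest.

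The cost is a recalculation and wording, with no new data. The downside is a less favourable stated figure and an SA comparison that opens later. On the mid-2022 count, no extra accrual is implied against Cohort 3 at 1:2, subject to eligibility losses.
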